### **2.2.2. Efficacy Endpoints (if dose expansion is conducted)**

- Primary Endpoint: Overall response rate (ORR)
- Secondary Endpoint: Duration of response (DOR), progression-free survival (PFS), overall survival (OS)

Disease response will be evaluated according to the European Leukemia Network (AML) ([Appendix 2](#)) and will include the following:

- **Overall response rate (ORR):** complete remission (CR), complete remission with incomplete hematologic recovery (CRi), morphologic leukemia-free state (MLFS), partial remission (PR).
- **Duration of response (DOR):** the duration of time from first meeting CR, PR, MLFS, CRi, measurement criteria (whichever occurs first) until the first date that progressive disease (PD) is objectively documented.
- **Progression-free survival (PFS):** the duration of time from date of first study treatment until the first date that disease progression is objectively documented or death due to any cause.
- **Overall survival (OS):** the duration of time from date of first study treatment until death from any cause.

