## 6.3. Efficacy Assessments

#### 6.3.1. Bone Marrow Aspirate and Biopsy

Bone marrow biopsy and aspirate will be taken within 30 days prior to first dose (baseline) for all AML patients. This will be repeated on cycle 1 day 8. It will again be repeated, for efficacy purposes according to the ELN criteria, at the conclusion of each cycle until the subject has achieved a MLFS, CRi or CR, or per investigator discretion. . It will also be performed as an end of treatment assessment if this occurs >30 days from another scheduled or unscheduled bone marrow biopsy. Bone marrow biopsies will also be performed at any time at the discretion of the investigator in accordance with standard of care (i.e. at the time of suspected progression, etc).

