#### 6.3.2. Response Assessments

Response assessments will occur at each bone marrow biopsy starting with cycle 1 day 28. Responses will be assessed per the ELN criteria (Appendix 2).

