### 7.2.1.      Events that Do Not Meet the Definition of a Serious Adverse Event

Elective hospitalizations to administer, or to simplify study treatment or study procedures (ie, an overnight stay to facilitate 24-hour urine collection) or other medical procedures are not considered SAEs. A ‘serious’ hospitalization is defined as any inpatient hospital admission that includes a minimum of an overnight stay in a health care facility. An emergency room visit is not considered a hospitalization unless it results in an official admission as in inpatient to the hospital (eg, undesirable effects of any administered treatment) and must be documented as an SAE. Progression of the AML (including fatal outcomes) should not be reported as an SAE during the study or within the safety reporting period (see Section 7.2.2). Sudden and unexplained death should be reported as an SAE. If there is any uncertainty about a finding being due solely to progression of malignancy, the finding should be reported as an AE or SAE, as appropriate.

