## 8. STATISTICAL METHODS

### 8.1. General Considerations

Tabulations will be produced for appropriate disposition, demographic, baseline, efficacy, and safety parameters. For categorical variables, summary tabulations of the number and percentage of patients within each category (with a category for missing data) of the parameter will be presented. For continuous variables, the number of patients, mean, median, standard deviation, minimum, and maximum values will be presented. Time-to-event data will be summarized using Kaplan-Meier methodology with median event time and associated 2 sided 95% confidence intervals, as well as number and percentage of patients with events and censored patients.

Patients who are in the Dose Escalation Phase being treated at the RP2D chosen for expansion will be included in the efficacy and safety assessment of the Dose Expansion Phase.

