### 8.5. Efficacy Analysis

- **Overall response rate (AML):** complete remission (CR), complete remission with incomplete hematologic recovery (CRi), morphologic leukemia-free state (MLFS), partial remission (PR).
- **Duration of response (DOR):** the duration of time from first meeting CR, PR, MLFS, CRi, measurement criteria (whichever occurs first) until the first date that PD recurrence is objectively documented.
- **Progression-free survival (PFS):** the duration of time from date of first study treatment until the first date that PD is objectively documented or death due to any cause.
- **Overall survival (OS):** the duration of time from date of first study treatment until death from any cause.
- **Time to Progression (TTP):** The duration of time from date of first study treatment until the first date that PD is objectively documented or death due to PD. Patients without documented PD will be censored on the date of last disease assessment.

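### Section 8.5 counts death due to PD as a TTP event, then censors every patient without documented PD, so a PD death with no documented PD is both an event and censored (minor)

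*Combined protocol and SAP*

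**What the plan says.** Section 8.5 (Efficacy Analysis) gives TTP in two sentences. The first runs the clock from first study treatment "until the first date that PD is objectively documented or death due to PD". The second is the censoring rule: "Patients without documented PD will be censored on the date of last disease assessment". TTP is the only endpoint in 8.5 with a written censoring rule.

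Other parts of the plan that bear on it:

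- Section 8.1 summarizes time-to-event data by Kaplan-Meier with medians and 95% confidence intervals, "as well as number and percentage of patients with events and censored patients".
- Section 6.3.2 ties disease assessment to marrows: "Response assessments will occur at each bone marrow biopsy starting with cycle 1 day 28". Section 6.3.1 schedules them "at the conclusion of each cycle until the subject has achieved a MLFS, CRi or CR, or per investigator discretion", and also at end of treatment if more than 30 days have passed since another marrow, and whenever the investigator judges, for example at suspected progression.
- Section 7.2.1 foresees deaths from leukemia: "Progression of the AML (including fatal outcomes) should not be reported as an SAE during the study".
- PFS in Section 8.5 runs "until the first date that PD is objectively documented or death due to any cause", so it counts all deaths.
- For the expansion, Section 2.2.2 names ORR as primary and then "Secondary Endpoint: Duration of response (DOR), progression-free survival (PFS), overall survival (OS". TTP is not listed there, in the synopsis table of objectives and endpoints, or in the synopsis efficacy endpoints.

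**The concern.** The two sentences classify the same patient differently. The first treats documented PD and death due to PD as alternative events. The second makes documented PD the sole condition for escaping censoring. A patient who dies of leukemia before PD is objectively documented meets the second event criterion and also falls under the censoring rule.

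A Kaplan-Meier analysis needs one status and one time per patient. If the censoring sentence is followed, the patients removed from the event count are those whose disease killed them. That censoring is informative, and it lengthens the estimated TTP. If the event sentence is followed, the same patients count at death. The choice would be left to whoever programs the analysis, possibly after the data have been seen.

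**Working it through.** **1. Classify each type of patient under the two sentences.**

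| Patient | Event sentence | Censoring sentence |
|---|---|---|
| PD documented, whether or not death follows | Event at documentation | Does not apply |
| No documented PD, death due to PD | Event at death | Censored at last assessment |
| No documented PD, death from another cause | Not an event | Censored at last assessment |
| No documented PD, alive | Not an event | Censored at last assessment |

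Only the second row conflicts. It is also the only row in which death due to PD can act as an event, because in the first row the clock has already stopped. The literal censoring sentence therefore gives that event type no effect.

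**2. One patient (hypothetical).** The day-28 marrow shows no PD, death attributed to AML follows on day 50, and PD is not documented in between. The event sentence gives an event at day 50. The censoring sentence gives censoring at day 28, which is 50 - 28 = 22 days earlier and with the opposite status.

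**3. Can such patients arise?** Yes. Scheduled marrows are about a cycle apart and need not continue after MLFS, CRi or CR. The end-of-treatment marrow is not required if one was done in the previous 30 days. Later follow-up (Table 3) records survival and response status every 3 months, with no marrow scheduled. Section 4.2 itself separates clinical progression from progression per response criteria. The documents do not say how many such patients to expect.

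**4. Size (illustration only).** The plan states no TTP figure, so there is none to reproduce. Let f be the share of progressions that are PD deaths without documented PD. The values of f are assumed.

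With constant total hazard h and these deaths censored at the time of death, the observed hazard is h(1-f), so the median is multiplied by 1/(1-f):

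- f = 10%: 1/0.9 = 1.11
- f = 20%: 1/0.8 = 1.25
- f = 30%: 1/0.7 = 1.43
- f = 40%: 1/0.6 = 1.67

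This formula is not the plan's rule, which censors earlier, at the last assessment. It also assumes continuous observation and a large sample.

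A simulation closer to the rule used 28-day assessments, exponential TTP with an assumed true median of 2 or 3 cycles, and all patients followed to event. The sample sizes were n = 10 (expansion alone) and n = 16 (10 plus up to 6 escalation patients at the RP2D, whom Section 8.1 includes). More are possible if lower-dose patients switch.

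| n | Events if PD deaths count | Mean events if censored, f = 10% to 40% | Typical median, true median 2 cycles | Typical median, true median 3 cycles |
|---|---|---|---|---|
| 10 | 10 | 9.0 to 6.0 | 2 becomes 2 to 4 | 3 becomes 3 to 5 |
| 16 | 16 | 14.4 to 9.6 | 2 becomes 3 to 4 | 3 becomes 4 to 5 |

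The event counts are n(1-f); for example, 16 x 0.9 = 14.4. Medians move mostly in whole cycles, so some typical values sit on a boundary and can differ by a cycle between runs. Within a single simulated trial the two rules often agree: they gave the same median in about 62% to 79% of trials at f = 10%, 37% to 60% at f = 20%, and 9% to 24% at f = 40%.

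**The case against.** The best defense is that the censoring sentence is the usual residual rule, meant for patients without a TTP event. Read that way, both sentences work, and a careful statistician would probably program it so. This is likely what the plan intends. It is not what the plan says: the first sentence sets documented PD and death due to PD apart as alternatives, and the second names only documented PD. Nothing elsewhere resolves the overlap.

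A reader might draw three stronger conclusions that the documents do not support:

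- *Every leukemia death without a confirmatory marrow is affected.* Section 8.5 requires objective documentation and does not say that a marrow is the only form. Section 6.3.1 allows a marrow at suspected progression, Section 5.7.3 treats new anti-tumor therapy as an indication of progression to be recorded, and Table 3 collects response status in follow-up. The affected group is PD deaths with no objectively documented PD, which may be small.
- *Median TTP will be overstated by 11% to 67%.* The values of f behind those figures have no source in the documents, and the formula censors at a different time from the rule.
- *Two analysts will get different medians.* They could. At low f and these sample sizes the median often does not change.

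It is also fair to say that rewording alone would not make TTP fully reproducible. Appendix 2 gives no criterion for PD, and no rule says how a death is attributed to PD. That stands, but it does not excuse the conflict.

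**Conclusion.** The TTP censoring sentence in Section 8.5 is wrong as written. For a death due to PD with no objectively documented PD, it contradicts the event definition immediately before it. Followed literally, it nullifies that event type and censors informatively, with an upward bias in TTP. This conclusion rests on the wording alone and needs no numerical assumption.

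The size cannot be fixed from the documents. If f were 10% to 40%, the typical median might move by anything from nothing to about two cycles, but those inputs are assumed.

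Severity is minor. TTP is descriptive, appears on no endpoint list and arises only if the optional expansion is conducted. It plays no part in the MTD, the RP2D or the sample size. A reader might infer that the other survival results are compromised, but PFS and OS count all deaths and do not contain this conflict.

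**What to change.** Change the subject of the censoring sentence in Section 8.5 so that it covers only patients with neither documented PD nor death due to PD, and leave the rest of the sentence as it is. Alternatively, delete TTP from Section 8.5: it is absent from the synopsis and Section 2.2.2 endpoint lists, and PFS already counts all deaths. If TTP is kept, it would help to state what counts as documented PD and how a death is attributed to PD.

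The cost is one sentence, with no added patients, visits or data. The downside is that the TTP estimate may be shorter than under the literal rule. The change should be made before efficacy data are examined, so that the choice between the two readings cannot depend on the result.

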### 8.6. Safety Analysis

All safety analyses will be made on the Safety Population.

The safety and tolerability of KPT-9274 will be evaluated by means of DLTs, AE reports, physical examination results, electrocardiogram results and laboratory safety evaluations. NCI CTCAE, Version 5.0 will be used for grading of AEs.

The MTD will be based on the assessment of DLTs during the first cycle of therapy and will be defined as the highest dose at which  $\leq 1$  patient experiences DLTs within Cycle 1.

Interim safety data will be examined on an ongoing basis to ensure patient safety.

### **8.6.1. Adverse Events**

Analyses of AEs will be performed for those events that are considered to be treatment-emergent AEs (TEAEs), defined as any AE with onset or worsening of a pre-existing condition on or after the first administration of study medication through 30 days following last dose or any event considered drug-related by the Investigator through the end of the study. Adverse events with partial dates will be assessed using the available date information to determine if treatment-emergent; AEs with completely missing dates will be assumed to be treatment-emergent.

Adverse events will be summarized by frequency counts at patient level. Tabulations will be provided for all TEAEs, for TEAEs assessed by the Investigator as at least possibly related to treatment, for  $\geq$  Grade 3 TEAEs, and for serious AEs (SAEs).

No formal hypothesis-testing analysis of AE incidence rates will be performed.

All AEs (treatment-emergent and post-treatment) will be listed in patient data listings. Separate by-patient listings will be provided for the following: patient deaths, SAEs, and AEs leading to withdrawal.

### **8.6.2. Clinical Laboratory Data**

Clinical laboratory values will be expressed using conventional SI units.

The actual value and change from Baseline for each on study evaluation will be summarized for each clinical laboratory parameter, including hematology and clinical chemistry.

Severity of select clinical lab measures will be determined using CTCAE criteria (i.e., those measures that have a corresponding CTCAE grade classification). Shift tables that present changes from baseline to worst on-study and baseline to last on-study values relative to CTCAE classification ranges will be produced.

### **8.6.3. Vital Signs and Examinations**

The actual value and change from baseline to each on-study evaluation will be summarized.

Physical examination results at Screening will be summarized; all other abnormal physical examination data are to be recorded on the AE eCRF. All examination findings will be presented in a data listing. ECOG performance status scores, and 12-lead ECG results will be summarized.

### **8.6.4. Concomitant Medications**

Concomitant medications will be tabulated based on the current version of the World Health Organization (WHO) Drug Dictionary.

## **9. ADMINISTRATIVE MATTERS**

### **9.1. Regulatory and Ethical Compliance**

This clinical study was designed and will be implemented and reported in accordance with the ICH Harmonised Tripartite Guidelines for Good Clinical Practice (GCP). Applicable local regulations, including European Directive 2001/20/EC and United States Code of Federal Regulations Title 21, and the ethical principles outlined in the Declaration of Helsinki will be followed.

### **9.2. Ethics Committees**

The protocol, the proposed ICF, and any other relevant records must be reviewed and approved by a properly constituted ethics committee (eg, IRB) before study start.

### **9.3. Regulatory Authority Approval**

Before implementing this study, the protocol must be approved by relevant, competent regulatory authorities.

### **9.4. Protocol Adherence**

Prior to study start, the Investigator is required to sign a protocol signature page confirming his/her agreement to conduct the study in accordance with the instructions and procedures found in this protocol and to give access to all relevant data and records to the drug supplier, Quality Assurance representatives, designated agents of the Sponsor-Investigator, ethics committees, and regulatory authorities as required. Investigators attest they will apply due diligence to avoid protocol deviations. All significant protocol deviations will be recorded and reported in the clinical study report (CSR). A significant protocol deviation is defined as any change to the execution of the protocol, that affects the scientific integrity or design of the study, or the rights, safety or welfare of study patients.

### **9.5. Amendments to the Protocol**

Any significant change or addition to the protocol by the Sponsor-Investigator can only be made in a written protocol amendment that must be provided by the Sponsor-Investigator, reviewed/approved by the drug supplier, and approved by Health Authorities where required, and the ethics committee (eg, IRB). Only amendments that are required for clarification or patient safety, by the Sponsor-Investigator, may be implemented prior to ethics committee (eg, IRB) approval. Notwithstanding the need for approval of formal protocol amendments, the Investigator is expected to take any immediate action required for the safety of any patient included in this study, even if this action represents a deviation from the protocol. In such cases, the Sponsor-Investigator should be notified of this action and the ethics committee (eg, IRB) at the study site should be informed according to local regulations but not later than 10 working days.

### **9.6. Informed Consent**

Eligible patients may only be included in the study after providing written (witnessed, where required by law, ethics committee [eg, IRB], or regulation), ethics committee (eg, IRB)-approved informed consent.

Informed consent must be obtained before conducting any study-specific procedures. Procedures that are part of the clinical routine evaluations during the initial diagnostic work-up of the patient may be performed before the ICF is signed and dated (ie, procedures that are not specific to the conduct of the study).

Informed consent must also be obtained for patients before conducting any study-specific procedures for treatment.

The process of obtaining informed consent should be documented in the patient source documents. A copy of the ICF must be given to the patient or to the person signing the form on behalf of the patient. The Investigator or designee must record the date when the study ICF was signed in the medical records of the patient. The name and role of the witness, if required, should also be documented.

The Sponsor-Investigator will provide to the drug supplier, in a separate document, a proposed ICF that is appropriate for this study and complies with the ICH GCP guideline and regulatory requirements.

## **9.7. Patient Confidentiality and Disclosure**

The Investigator must ensure anonymity of all patients; patients must not be identified by names in any documents submitted to the drug supplier or its designee. Signed ICFs and patient enrollment logs must be kept strictly confidential.

## **9.8. Collection, Auditing Study Documentation, and Data Storage**

### **9.8.1. Study Documentations, Record Keeping and Retention of Documents**

Each participating site will maintain appropriate medical and research records for this study, in compliance with Section 4.9 of ICH E6 GCP, and according to the regulatory and institutional requirements.

Source data include all information, original records of clinical findings, observations, or other activities in a clinical study necessary for the reconstruction and evaluation of the study.

Data collection is the responsibility of the clinical study staff at the site under the supervision of the site Investigator. The study database is the primary data collection instrument for the study. The Investigator is responsible for the accuracy, completeness, and timeliness of the data reported in the database and all other required reports. Data reported in the database, which are derived from source documents, should be consistent with the source documents or the discrepancies should be explained. All data requested on the source documents must be recorded. Any missing data must be explained. If electronic records are used, an audit trail will be maintained by the system, in compliance with 21 CFR Part 11.

The Investigator/institution should maintain study documents as specified in Essential Documents for the Conduct of a Clinical Trial (ICH E6 Section 8) and as required by applicable regulations and/or guidelines. The Investigator/institution should take measures to prevent accidental or premature destruction of these documents.

Essential documents (written and electronic) should be retained for a period of not less than 15 years from the completion of the clinical study unless the Sponsor provides written permission to dispose of them or, requires their retention for an additional period of time because of applicable laws, regulations, and/or guidelines.

### **9.8.2. Monitoring and Oversight**

The sponsor investigator will be responsible for monitoring the trial per the trial monitoring plan, in addition to overseeing the safety and efficacy of the trial including any specimens collected, executing the data and safety monitoring (DSM) plan, and complying with all reporting requirements to local and federal authorities. This oversight will be accomplished through additional oversight from the Data and Safety Monitoring Committee (DSMC) at the University of Colorado Cancer Center (CU Cancer Center). The DSMC is responsible for ensuring data quality and study participant safety for all clinical studies at the CU Cancer Center, which is the coordinating institution of this trial.

A summary of the DSMC's activities is as follows:

- Conduct of internal audits
- Ongoing review of all serious adverse events (SAEs) and unanticipated problems (UAPs)
- May submit recommendations for corrective actions to the CU Cancer Center's Executive Committee

Per the CU Cancer Center Institutional DSM Plan, SAEs and UAPs are reported to the DSMC, IRB and the sponsor investigator per protocol. All SAEs and UAPs are to be reported to the DSMC within 7 (for fatal or life-threatening events) or 15 (non-life-threatening events) calendar days of the sponsor investigator receiving notification of the occurrence.

Each subject's treatment outcomes will be discussed by the site PI and appropriate staff at regularly scheduled meetings. Data regarding number of subjects, significant toxicities, dose modifications, and treatment responses will be discussed and documented in the meeting's minutes.

The sponsor investigator will provide a DSM progress report to the CU Cancer Center DSMC on a recurring basis (either every six or twelve months based on DSMC vote). The DSM report will include a protocol summary, current enrollment numbers, summary of toxicity data to include specific SAEs, UAPs and AEs, any dose modifications, all protocol deviations, and protocol amendments. The DSM progress report submitted to the DSMC will also include, if applicable, the results of any efficacy data analysis conducted. Results and recommendations from the review of this progress report by the DSMC will then be provided to the sponsor investigator in a DSMC review letter. The sponsor investigator is then responsible for ensuring this letter is submitted to the site's IRB of record at the time of IRB continuing review.

